3 STUDY DESIGN

3.1 OVERVIEW

This is a Phase IIa, eight-week, double-blind, placebo-controlled randomised study aimed at evaluating the safety and efficacy of ABX464 given once a day (o.d.) at 50 mg, followed by a one-month follow-up

period, in subjects with moderate to severe active ulcerative colitis (UC), who have failed or are intolerant to immunomodulators, anti-TNF α , vedolizumab and/or corticosteroids.

Eligible subjects will be recruited to up to 20 sites in France, Belgium, Poland, Germany, Austria and Hungary from Q3 2017 – Q2 2018 during the overall study period of Q2 2017 – Q3 2018. A total of 30 subjects will be randomised using a 2:1 ratio, where for every two subjects randomised to receive ABX464, one subject will be randomised to receive placebo. Thus 20 subjects will be randomised to receive ABX464 and 10 subjects will be randomised to receive placebo. Randomisation will be stratified according to concomitant treatment with corticosteroids (yes, no) and previous biologics exposure (yes, no).

The dose of 50 mg of the study drug has been selected based on the reassuring safety data accumulated on the 50 mg o.d. from previous studies and the high exposure in ABX464-NGluc (active metabolite) at this dose. A Data Safety Monitoring Board (DSMB) will meet after every three subjects are recruited in order to review the safety profile of this dose level on a regular basis and to recommend, if appropriate, the continuation of the study.

The total duration of the study will be approximately 11 weeks. Subjects will be enrolled at a screening visit, two weeks prior to the first dosing, and eligible subjects will be treated for a total of eight weeks. All subjects willing to continue with the study treatment will be able to take part in a follow-up open-label study, ABX464-102. Subjects who do not enter the open-label study will exit the study and need to perform their end of study (EoS) visit within a week after the last dosing. These subjects will be treated according to the standard of care.

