3.4 STUDY TIME POINTS

A screening visit will occur at Day -14, where procedures and laboratory tests are performed to determine eligibility of subjects. The Investigator will need to check the results of these procedures and if they are in line with the inclusion and exclusion criteria then the subject will be randomised. Note that the process of randomisation does not require a site visit by the subject.

At Day 0, study drug (ABX464 or its matching placebo) will be administered once a day at 50 mg for the next 56 days. Subjects will be seen at the site every week during the first month of treatment (Day 7, 14, 21 and 28) and then every two weeks during the second month (Day 42 and 56).

At Day 56, all subjects willing to carry on the study treatment will be able to take part in an open-label study (ABX464-102). In any other cases, the subjects will perform an EoS visit within a week after last dosing (Day 63). Subjects will be treated according to the standard of care since the last day of study treatment. The total duration of the study participation is 11 weeks.

Visits and visit windows will be as follows:

Visit	Day	Window
Screening	-14	± 3 days
Rand	lomisation	
Baseline/ First dose date	0	
	7	± 2 days
	14	± 2 days
Tuestus out a suis d	21	± 2 days
Treatment period	28	± 2 days
	42	± 4 days
	56	± 4 days
Enter follow-up study ABX464-1	02 or exit study an	d perform EoS visit
EoS	63	± 2 days

If more than one visit occurs within a window, the nearest to the scheduled time will be presented within the summaries.

See Section 16.1 for the Study Flow Chart.

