6.2 SAFETY SET

The Safety Set is defined as all patients who receive at least one dose of study treatment.

The Safety Set will be used for all safety analyses. Patients who receive the wrong treatment in error will be analysed as treated for safety analyses.

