11.4 SAFETY ANALYSES

11.4.1 Adverse Events

All AEs will be classified using the version of the MedDRA coding dictionary specified in the DMP.

Events will be classified as treatment-emergent if they started or increased in severity on or after the first date and time of medication dosing at Day 0 and up to study closure or withdrawal date. If an event start date is partial, then the start day, month, year or stop date will be used to determine if the event is treatment-emergent. If the classification of the AE cannot be determined from the data available, then the event will be considered treatment-emergent.

An overall summary table will be presented for AEs occurring from baseline to the end of the study in the following categories (*Table 14.3.1.1*):

- Any adverse event;
- Any TEAE;
- Any serious adverse event (SAE);
- Any severe adverse event (Common Toxicity Criteria [CTC] grade 3 or 4);
- Death

The primary safety endpoint, the rate of all TEAEs will be compared between the treatments by stratified likelihood ratio chi-square test on a 10% one-sided significance level and presented in the same table.

TEAEs will be further classified as follows:

Severe TEAEs: Severity classified as 'severe' (Common Toxicity Criteria [CTC] grade 3 or 4) or missing.

Serious TEAEs: Serious classified as 'yes' or missing.

Drug-related TEAEs: Relationship to study drug classified as 'yes' or missing.

Serious drug-related TEAEs: Both serious and drug-related, as specified above.

TEAEs leading to study drug discontinuation: Action taken classified as 'permanent discontinuation'.

TEAEs overall and in each of the above classifications will be summarised separately for the following periods (Tables 14.3.1.2.1 and 14.3.1.2.2):

- Period 1: Adverse event occurs or worsens from first dosing to Day 56
- Period 2: Adverse event occurs after Day 56

Summaries by SOC and PT will also be presented for TEAEs in the two periods (*Tables 14.3.1.3.1.1* and 14.3.1.3.1.2). Similar tables will be presented for each of the classifications of treatment-emergent events above (*Tables 14.3.1.3.2.1* and 14.3.1.3.6.2).

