	Minimum	xx.x	xx.x
	Maximum	xx.x	xx.x
Week 4	N	xx	xx
	Mean	xx.xx	xx.xx
	Etc		
Change from baseline to Week 4	N	xx	xx
	Mean	xx.xx	xx.xx
	Etc		
Week 8	N	xx	xx
	Mean	xx.xx	xx.xx
	Etc		
Change from baseline to Week 8	N	xx	xx
-	Mean	xx.xx	xx.xx

Version date: 23 August 2018

Etc

Repeat for physical health component summary measure on a new page

Source: Listing 16.x.x Path\Filename

Page x/y

Table 14.3.1.1 Summary of Adverse Events (Safety Set)

ddMMMyyyy

	ABX-464 (N=xx)		Placebo (N=xx)		Total (N=xx)		N=xx)	p-value*
	n	N (%)	n	N (%)	n	N (%)	
Any Adverse Event	xx	xx (xx.x%)	xx	xx (xx.x%)	xx	xx (x	x.x%)	
Any Treatment-Emergent Adverse Event	xx	xx (xx.x%)	xx	xx (xx.x%)	xx	xx (x	x.x%)	x.xxxx
Any Serious Adverse Event	xx	xx (xx.x%)	xx	xx (xx.x%)	xx	xx (x	x.x%)	
Any Severe Adverse Event	xx	xx (xx.x%)	xx	xx (xx.x%)	xx	xx (x	x.x%)	
Adverse Event leading to death	xx	xx (xx.x%)	xx	xx (xx.x%)	xx	xx (x	x.x%)	

The table presents number of events (n) and number and percentage of patients (N(%)) The denominator for each percentage is the number of patients within the column

*TEAE rate between treatments is compared using stratified likelihood ratio chi-square test at a one-sided 10% significance level.

Source: Listing 16.x.x

Path\Filename

Page x/y

Version date: 23 August 2018

Page 49 of 93

ddMMMyyyy
Table 14.3.1.2.1 Summary of Treatment-Emergent Adverse Events: Period 1 (Safety Set)

	ABX-464 (N=xx)		Placebo (N=xx)		Total (N=x	
	n	N (%)	n	N (%)	n	N (%)
Treatment-Emergent Adverse Events	××	xx (xx.x%)	xx	xx (xx.x%)	xx	xx (xx.x%)
Severe Treatment-Emergent Adverse Events	xx	xx (xx.x%)	xx	xx (xx.x%)	xx	xx (xx.x%)
Serious Treatment-Emergent Adverse Events	xx	xx (xx.x%)	xx	xx (xx.x%)	xx	xx (xx.x%)
Drug-Related Treatment-Emergent Adverse Events	xx	xx (xx.x%)	xx	xx (xx.x%)	xx	xx (xx.x%)
Serious Drug-Related Treatment-Emergent Adverse Events	xx	xx (xx.x%)	xx	xx (xx.x%)	xx	xx (xx.x%)
freatment-Emergent Adverse Events leading to Study Drug Discontinuation	xx	xx (xx.x%)	××	xx (xx.x%)	xx	xx (xx.x%)

The table presents number of events (n) and number and percentage of patients (N(%)) The denominator for each percentage is the number of patients within the column

Source: Listing 16.x.x Path\Filename

This layout also applies to : Table 14.3.1.2.2 Summary of Treatment-Emergent Adverse Events: Period 2 (Safety Set) Page x/y

Version date: 23 August 2018

Page 50 of 93

ABX464-101 ddMMMyyyy

Table 14.3.1.3.1.1 Treatment-Emergent Adverse Events, by SOC and PT: Period 1 (Safety Set)

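### Period 2 adverse-event percentages divide by everyone treated, with no rule for subjects who enter ABX464-102, and the periods are cut at Day 56 instead of last dose

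*SAP*

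**What the plan says.** SAP 11.4.1 defines two TEAE periods: "Period 1: Adverse event occurs or worsens from first dosing to Day 56" and "Period 2: Adverse event occurs after Day 56". Protocol 9.3 has the same two. Neither mentions last dose or says whether Day 56 is study day 56 or the Day 56 visit.

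The Period 2 overview, Table 14.3.1.2.2, takes the Period 1 layout and population. Its title is "Summary of Treatment-Emergent Adverse Events: Period 2 (Safety Set") and its footnote is "The denominator for each percentage is the number of patients within the column". The same footnote governs the six Period 2 tables by system organ class and preferred term and the Period 2 intensity table, so eight Period 2 tables are affected. On the population, SAP 6.2 says "The Safety Set is defined as all patients who receive at least one dose of study treatment".

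On roll-over, SAP 3.1 says "All subjects willing to continue with the study treatment will be able to take part in a follow-up open-label study, ABX464-102". SAP 3.1 and 3.4, and protocol 3.2 and 5.2.6, give the end-of-study (EoS) visit to the remaining subjects. Protocol 7.3 asks all subjects for that visit. Protocol 8.4 requires adverse events to be recorded until 4 weeks after the product is completed or stopped, with no exception for roll-over. SAP 11.4.1 counts events as treatment-emergent "on or after the first date and time of medication dosing at Day 0 and up to study closure or withdrawal date" and does not say whether entering ABX464-102 closes that window.

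**The concern.** A percentage for a follow-up period should rest on the subjects followed in it. Here the denominator is fixed at first dose and takes no account of who remains under observation after Day 56. A reader of a Period 2 table cannot tell a low event rate from a small observed group. If roll-over differs between arms, equal risks would print as unequal percentages.

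The cut raises a separate problem. The natural reading of a split at the end of an 8-week treatment course is on-drug against off-drug. A split at Day 56 does not deliver that for subjects who stop early and may not for subjects whose Day 56 visit is late. Safety is the primary objective and the arms are 20 and 10, so a few subjects visibly change a percentage.

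**Working it through.** The plan states no Period 2 rate, roll-over share or number at risk, so there is no figure of its own to reproduce.

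**Step 1. Who is observed after Day 56?**

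- Reading A (SAP 3.1 and 3.4; protocol 3.2 and 5.2.6): roll-over subjects have no further ABX464-101 visit, so they can hardly contribute a Period 2 event.
- Reading B (protocol 7.3 and 8.4): every subject has the EoS visit, and events are recorded for 4 weeks after the product is completed or stopped.

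The documents do not choose between them.

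**Step 2. Denominator under Reading A.** Let p be the risk among those observed and r the roll-over share. Expected printed percentage = p × N(1 − r) / N = p(1 − r). Assume p = 20% and take N = 20 (ABX464 arm, SAP 3.1). The last column instead fixes the count at 2 subjects with an event, which the layout always prints as 2/20 = 10.0%.

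| Assumed r | Observed | Expected with event | Printed (÷ 20) | 2 subjects ÷ observed |
|---|---|---|---|---|
| 0% | 20 | 4 | 20% | 10.0% |
| 25% | 15 | 3 | 15% | 13.3% |
| 50% | 10 | 2 | 10% | 20.0% |
| 75% | 5 | 1 | 5% | 40.0% |

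Subjects who withdrew before Day 56 act like extra roll-overs here: their TEAE window closes at withdrawal, yet they stay in N.

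**Step 3. Between arms under Reading A.** With p = 20% in both arms, r = 50% on ABX464 and 80% on placebo gives 20% × 0.5 = 10% against 20% × 0.2 = 4%. Swapping the shares gives 4% against 10%. Equal shares scale both arms alike and leave their ratio unchanged.

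**Step 4. Reading B.** The dilution from roll-over goes away, but an event that starts on open-label treatment in the weeks after Day 56 is tabulated under the arm assigned in ABX464-101.

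**Step 5. The cut.** Take Day 56 as the study day (SAP section 5 counts the first dose as Day 0). Let L be the day of last dose and F the follow-up: 28 days (protocol 8.4) or 7 days (EoS visit). Off-drug days falling in Period 1 = min(F, max(0, 56 − L)). On-drug days falling in Period 2 = max(0, L − 56).

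| L | Off-drug days in Period 1, F = 28 | Off-drug days in Period 1, F = 7 | On-drug days in Period 2 |
|---|---|---|---|
| Day 28 | 28 of 28 | 7 of 7 | 0 |
| Day 42 | 14 of 28 | 7 of 7 | 0 |
| Day 52 | 4 of 28 | 4 of 7 | 0 |
| Day 56 | 0 | 0 | 0 |
| Day 60 | 0 | 0 | 4 |

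Day 60 is the edge of the ±4-day visit window, and protocol 7.1 continues treatment until that visit. Its 4 on-drug days would be 4 of 32 Period 2 days (F = 28) or 4 of 11 (F = 7). Protocol 6.4 dispenses 2 × 30 = 60 capsules, which cover Days 0 to 59 if none is missed, so 3 days is the more usual ceiling.

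**The case against.** A reader might infer that the Period 2 tables understate post-treatment rates. The documents do not support that as a general statement, for three reasons.

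- Non-observation of roll-over subjects is implied by the visit plan but contradicted by protocol 7.3 and 8.4. If those sections govern, the fault is contamination by open-label events.
- The cut has no fixed direction. Early stoppers move events out of Period 2, and late Day 56 visits can move on-drug events into it. If Day 56 means the visit, the cut lies near last dose for completers and only early stoppers are affected. Even for them the misplaced time may be short, because the TEAE window closes at withdrawal and protocol 5.2.6 has the EoS examinations done at premature discontinuation.
- Neither document calls Period 2 a post-treatment period.

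The consequence is also bounded. The primary TEAE comparison in Table 14.3.1.1 is not split by period. The Period 2 tables carry no test and print event and subject counts beside each percentage. Onset dates (Listing 16.2.7) and last-dose dates (Listing 16.2.5) would allow the events to be re-cut. Every roll-over share used above is assumed, and at 0% there is no dilution from roll-over.

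All of this stands as a limit on direction and size. It does not rescue the rule: the percentage is faulty under Reading A whenever anyone rolls over, and under Reading B whenever open-label events are recorded. The printed counts help with the numerator only, since the number observed appears nowhere in these tables.

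**Conclusion.** The point holds in limited form. The Period 2 denominator ignores who is observed, the follow-up of roll-over subjects is unresolved, and the cut is not tied to last dose.

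Under Reading A the percentage is multiplied by (1 − r): unchanged at r = 0, halved at 50%, a quarter at 75%. The arms are distorted relative to each other only if r differs between them. Under Reading B the size depends on open-label events and cannot be computed from the documents. The cut can shift anything from no time to the whole off-drug window of an early stopper into Period 1, and at most a few on-drug days into Period 2.

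These figures rest on an assumed 20% risk and assumed roll-over shares, and they are expectations: with 20 subjects the smallest non-zero percentage a table can print is 5%. The denominator and the cut affect descriptive tables and do not enter the primary TEAE test. The change should be made, but the trial's main safety comparison does not turn on it.

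**What to change.** - In SAP 11.4.1, the Period 2 table shells and protocol 9.3, define Period 1 as first to last dose of randomised study drug. Define Period 2 as after last dose to the last ABX464-101 contact, ending at entry into ABX464-102.
- Use the number per arm actually observed after last dose as the Period 2 denominator. Print it in the column header with the Safety Set N beside it.
- Label the between-arm reading of Period 2 as descriptive, because the subjects observed are self-selected.
- Reconcile SAP 3.1 and 3.4 and protocol 3.2 and 5.2.6 with protocol 7.3 and 8.4 on adverse-event follow-up of subjects who roll over.

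The cost is SAP wording, reprogrammed denominators for eight tables and a matching wording change in protocol 9.3. The roll-over date must be available. ABX464-102 is a separate protocol, and SAP 9.2 expects no external data beyond the central laboratory's, so the date has to be in the ABX464-101 record or be requested. The price is a small, non-randomised denominator, which is why the Safety Set N should stay in view.

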16 APPENDICES

16.1 STUDY FLOW CHART

STUDY FLOW CHART			than the first trial regions of the relative to Study Treatment Period in the first request the first state of								
	D-14	Rondomization D-	D0	D7	Ð14	D21	D28	D42	D56	D63- EOS	
Time Window	±3 days	± 3 days		± 2 days	± 2 days	± 2 days	± 2 days	± 4 days	± 4 days	± 2 days	
Obtained Inform Consent	X			1							
Check of IN/EX Criteria	X	X							i		
Physical Examination	Х		X	X	X	X	Х	X	X	Х	
Body Weight (kg)	Х		×	X	X	Х	X	X	X	X	
Height Measurement (cm)	Х										
Medical History and Concomitant Medications	х										
Vitel signs	Х		X	X	Х	X	X	X	X	Х	
ECG (12 lead)	Х		×				Х		X	Х	
Randomization		Х									
Blood Pregnancy test wocen	X		X				X		X		
Hematology • Blochemistry	X		Х	Х	X		X		X	Х	
Mayo score (Total or Partial)	Х		Х	X	Х	Х	Х	Х	X	Х	
Faecal calprotectin			×				х		X	×	
Rectal microbiota	X								×		
Sigmoldoscopy	Х								X		
SF-36 (Questionnaire)			Х				X		X		
ABX464/placebo treatment dispensation and subject diary review			Х				X				
Blood samples drug pK			x.	T			X,				
Samples for miRNA (Paxgene tubes/RNA-Later)			Х				×		х		
Adverse Events recording			X	X	X	Х	X	X	X	Х	

^{*} Applicable to the first 9 subjects randomized / PK predose, 0.5, 1, 1.5, 2, 2.5, 3, 4, 8 and 12 post-dose

Version date: 23 August 2018
